3.3 Additional Efficacy Endpoint(s)

The primary and secondary efficacy endpoints are listed in Section 3.1 and Section 3.2, respectively. The additional efficacy endpoints are:

Induction Period 1

- The achievement of SFS = 0, RBS = 0, and endoscopic subscore = 0 at Week 12
- The achievement of SFS \leq 1 at Week 4, Week 8, Week 12 respectively
- The achievement of RBS = 0 at Week 4, Week 8, Week 12 respectively
- The achievement of clinical response per Partial Adapted Mayo score at Week 8, Week 12 respectively
- Change from Baseline in Partial Adapted Mayo score at Week 4, Week 8, Week 12 respectively
- Change from Baseline to Week 12 in Full Mayo score
- Change from Baseline in SFS at Week 4, Week 8, Week 12 respectively
- Change from Baseline in RBS at Week 4, Week 8, Week 12 respectively

- Change from Baseline in hs-CRP at Week 4, Week 8, Week 12 respectively
- Change from Baseline in FCP at Week 4, Week 12 respectively
- Change from Baseline to Week 12 in UCEIS
- The achievement of histologic remission at Week 12
- Change from Baseline to Week 12 in European Quality of Life 5 Dimensions (EQ-5D-5L)
- Change from Baseline to Week 12 in Work Productivity and Impairment Questionnaire – UC (WPAI-UC)
- Change from Baseline to Week 12 in UC-SQ
- The achievement of IBDQ remission (IBDQ total score ≥ 170) at Week 12
- The achievement of IBDQ response (increase of IBDQ ≥ 16 from Baseline) at Week 12
- Time to clinical response per Partial Adapted Mayo
- Change from baseline in PGIS at Week 4, Week 8, Week 12 respectively
- PGIC at Week 4, Week 8, Week 12 respectively
- Occurrence of UC-related surgeries through Week 12
- The achievement of clinical response per Adapted Mayo score at Week 12 in subjects with pancolitis at Baseline
- Change from Baseline to Week 12 in Short Form-36 (SF-36)
- The achievement of clinical remission per Full Mayo score at Week 12 in subjects with a Full Mayo score of 6 to 12 at Baseline

Induction Period 2

- The achievement of clinical remission per Adapted Mayo at Week 24
- The achievement of clinical remission per Full Mayo score at Week 24 in subjects with a Full Mayo score of 6 to 12 at Baseline
- The achievement of clinical response per Adapted Mayo score at Week 24
- The achievement of no abdominal pain at Week 24
- The achievement of no bowel urgency at Week 24
- The achievement of endoscopic remission at Week 24

- The achievement of endoscopic improvement at Week 24
- Change from Baseline to Week 24 in Inflammatory Bowel Disease Questionnaire (IBDQ) total score
- Change from Baseline to Week 24 in Functional Assessment of Chronic Illness Therapy-Fatigue (FACIT-Fatigue)
- The achievement of histologic endoscopic mucosal improvement at Week 24
- The achievement of no nocturnal bowel movements at Week 24
- The achievement of no tenesmus at Week 24
- Change from Baseline to Week 24 in number of fecal incontinence episodes per week
- Change from Baseline to Week 24 in number of days per week with sleep interrupted due to UC symptoms
- The achievement of clinical response per Adapted Mayo score at Week 24 in subjects with pancolitis at Baseline
- Occurrence of UC-related hospitalizations through Week 24
- Change from Baseline to Week 24 in Short Form-36 (SF-36)
- The achievement of SFS ≤ 1 at Week 16, Week 20, Week 24 respectively
- The achievement of RBS = 0 at Week 16, Week 20, Week 24 respectively
- Change from Baseline in Partial Adapted Mayo score at Week 16, Week 20, Week 24 respectively
- Change from Baseline in SFS at Week 16, Week 20, Week 24 respectively
- Change from Baseline in RBS at Week 16, Week 20, Week 24 respectively
- Change from Baseline in hs-CRP at Week 24
- Change from Baseline in FCP at Week 24
- Time to clinical response per Partial Adapted Mayo
- Change from baseline in PGIS at Week 16, Week 20, Week 24 respectively
- PGIC at Week 16, Week 20, Week 24 respectively

3.4 Safety Endpoint(s)

The following endpoints will be included in the safety analyses:

- Treatment emergent adverse events (TEAEs)
- Areas of Safety Interest (ASIs)
- Laboratory tests
- Vital signs.

4.0 Analysis Populations

The following population sets will be used for the statistical analyses:

Intent-to-Treat Population

Sub-Study 2 Induction Period 1:

ITT2 includes all randomized subjects who received at least one dose of study drug during Induction Period 1. The **ITT2** will be used for all efficacy analysis, and demographic and baseline characteristics summary for Induction Period 1. Subjects will be included in the analysis according to the treatment groups that they are randomized to.

Sub-Study 2 Induction Period 2:

ITT2_P2 includes all subjects who received at least one dose of risankizumab during Induction Period 2 from Sub-Study 2. Subjects will be included in the analysis according to the treatment groups that they are re-randomized to the Induction Period 2 and the subjects who received placebo induction treatment during 12-Week Induction Period 1 and entered the Induction Period 2 will be also included (denoted as placebo/risankizumab). This analysis population will be used for efficacy analysis in Induction Period 2.

Safety Analysis Set

The safety analysis will be based on the corresponding safety analysis sets. Subjects will be analyzed in a treatment group based on the actual treatment received.

Sub-Study 2 – Induction Period 1

SA2 consists of all subjects who received at least one dose of study drug during Induction Period 1 in Sub-Study 2.

Sub-Study 2 Induction Period 2:

SA2_P2 consists of all subjects who received at least one dose of risankizumab during the Induction Period 2 after Week 12 in Sub-Study 2.

All Risankizumab:

SA2_ALL includes all subjects who received at least one dose of risankizumab any time during the Sub-Study 2.

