Approximately 966 subjects who meet all of the inclusion criteria and none of the exclusion criteria will be randomized into the double-blind 12-week study in a 2:1 ratio to one of the following treatment groups:

- Group 1: Risankizumab 1200 mg IV Weeks 0, 4, 8 (n = 644)
- Group 2: Placebo IV Weeks 0, 4, 8 (n = 322)

The randomization at baseline will be stratified by number of prior failed biologic treatments (0, 1 vs > 1), baseline steroid use (yes vs no), and baseline Adapted Mayo score (≤ 7 vs > 7). Endoscopy and the primary analyses will occur at Week 12. Subjects in Sub-Study 2 who achieve clinical response after completion of the 12-week Induction Period 1 will be enrolled into maintenance Study M16-066.

Subjects who do not achieve clinical response per Adapted Mayo score (locally read Mayo endoscopic subscore) at Week 12 may be eligible to receive blinded risankizumab treatment in Induction Period 2 as specified below. Subjects are not eligible to enter Induction Period 2 until the Week 12 endoscopy has been completed.

Induction Period 2:

At Week 12, subjects who do not achieve clinical response will be randomized by IRT to Induction Period 2, a double-blind, double-dummy 12-week treatment period to evaluate reinduction with risankizumab versus starting maintenance dosing on clinical response status.

Subjects who received IV risankizumab will be randomized 1:1:1 to:

- Group 1: 1200 mg IV risankizumab Weeks 12, 16, and 20
- Group 2: 360 mg SC risankizumab Weeks 12, and 20
- Group 3: 180 mg SC risankizumab Weeks 12, and 20

The randomization in Period 2 will be stratified by number of prior failed biologic treatments (0, 1 vs > 1), baseline steroid use (yes vs no), and baseline Adapted Mayo score (≤ 7 vs > 7).

Subjects who received placebo induction treatment will receive:

- Group 4: 1200 mg IV risankizumab Weeks 12, 16, and 20

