Endoscopy and efficacy evaluation will occur at Week 12. Subjects in Sub-Study 2 who achieve clinical response per Adapted Mayo score (locally read Mayo endoscopic sub score) after completion of the 12-week Induction Period 1 will be enrolled into maintenance Study M16-066. Subjects who do not achieve clinical response at Week 12, may be eligible to enter a blinded risankizumab treatment in Induction Period 2 as specified below.

Subjects are not eligible to enter Induction Period 2 until the Week 12 endoscopy has been completed, except in case of COVID-19 pandemic restrictions or geo-political conflict in Ukraine and surrounding impacted regions:

If endoscopy cannot be performed at Week 12 due to COVID-19 pandemic restrictions or geo-political conflict in Ukraine and surrounding impacted regions, clinical response will be calculated using the Partial Adapted Mayo score.

Subjects with missing endoscopy due to COVID-19 pandemic restrictions or geo-political conflict in Ukraine and surrounding impacted regions and achieve clinical response per

Partial Adapted Mayo score at Week 12 may be eligible to enroll in Study M16-066 Sub-Study 3, which is an open-label long term extension study to evaluate long-term safety of risankizumab. Subjects who do not achieve clinical response at Week 12, may be eligible to enter a blinded risankizumab treatment in Induction Period 2 as specified below.

Sub-Study 2 Induction Period 2:

At Week 12, subjects who do not achieve clinical response will be randomized by Interactive Response Technologies (IRT) to Induction Period 2, a double-blind, double dummy 12-week treatment period to evaluate reinduction with risankizumab versus starting maintenance dosing on clinical response status.

[figure not shown]
Subjects who received IV risankizumab will be randomized 1:1:1 to:

- Group 1: Risankizumab 1200 mg IV Weeks 12, 16, and 20
- Group 2: Risankizumab 360 mg SC Weeks 12, and 20
- Group 3: Risankizumab 180 mg SC Weeks 12, and 20

Subjects who received placebo induction treatment will receive:

- Group 4: Risankizumab 1200 mg IV Weeks 12, 16, and 20

The schematic of the Induction Period 2 is shown in [Figure 2](#).

Figure 2. Study Schematic of Induction Period 2

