3.0 Endpoints

Below are the endpoint definitions for efficacy variables:

- Mayo Score
 - Full Mayo Score: composite score of UC disease activity based on the
 - stool frequency subscore [SFS] (0 – 3), rectal bleeding subscore [RBS] (0 – 3), physician's global assessment [PGA] subscore (0 – 3) and endoscopic subscore (0 – 3). The endoscopic subscore will be based on central readings after adjudication (when applicable). The Full Mayo score ranges from 0 – 12 points with higher scores representing more severe disease.
 - Partial Mayo Score: Full Mayo score excluding the endoscopic subscore.
 - Adapted Mayo Score: Full Mayo score excluding the PGA subscore.
 - Partial Adapted Mayo Score: Adapted Mayo score excluding the endoscopic subscore.
- Clinical Remission per Adapted Mayo: stool frequency subscore (SFS) ≤ 1 , and not greater than baseline, rectal bleeding subscore (RBS) = 0, and endoscopic subscore ≤ 1 without the evidence of friability
- Clinical Response per Adapted Mayo: decrease from Baseline ≥ 2 points and $\geq 30\%$, PLUS a decrease in RBS ≥ 1 or an absolute RBS ≤ 1
- Clinical Response per Partial Adapted Mayo (without endoscopy): decrease from Baseline ≥ 1 points and $\geq 30\%$, PLUS a decrease in RBS ≥ 1 or an absolute RBS ≤ 1
- Clinical Remission per Full Mayo: Full Mayo score ≤ 2 with no subscore > 1

- Endoscopic Improvement: endoscopy subscore of 0 or 1 without the evidence of friability
- Endoscopic Remission: endoscopic subscore = 0
- Histologic Remission: Geboes score of < 2.0
- Histologic Endoscopic Mucosal Improvement (HEMI): Endoscopic subscore of 0 or 1 without the evidence of friability and Geboes score \leq 3.1.
- Histologic Endoscopic Mucosal Remission (HEMR): Endoscopy subscore of 0 and Geboes score < 2.0

Note: Evidence of friability during endoscopy in subjects with otherwise "mild" endoscopic activity will confer an endoscopic subscore of 2.

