8.0 Handling of Potential Intercurrent Events

The primary efficacy endpoint of clinical remission per Adapted Mayo score at Week 12 (defined in Section 3.1) and the secondary efficacy endpoints (defined in Section 3.2) will be analyzed based on the ITT2 population. The following methods will be used to address potential intercurrent events (IEs):

- IE1. Premature discontinue from the study drug:
 - Data collected will be used regardless of premature discontinuation of study drug.
- IE2. Initiation or dose escalation of UC-related corticosteroid event defined as:
 - Subjects not on UC-related corticosteroids (systemic or locally acting corticosteroids for UC) at baseline who then initiated UC-related corticosteroids during the Induction study.
 - Subjects on UC-related systemic corticosteroids at baseline who have dosages increased to greater than the prednisone equivalent dose of corticosteroid taken at baseline, or initiation of any rectal corticosteroids during the Induction study regardless of rectal corticosteroid dose.
 - Subjects on UC-related rectal corticosteroids at baseline who have dosages increased to greater than the dose taken at baseline, or initiation of any new type of rectal or any systemic corticosteroids during the Induction study.

The time point of the UC-related corticosteroids intercurrent event is defined as the date when one of the scenarios above occurs for a subject. As such, subjects will be considered as "non-responder" for binary endpoints on or after the date of the UC-related corticosteroids intercurrent event through the end of the Induction study in the primary analysis (except for the occurrence of UC-related hospitalization and UC-related surgeries). For continuous endpoints, all measurements on or after the date of the UC-related corticosteroids intercurrent event through the end of the Induction study will not be used in the primary analysis.

- IE3. UC-Related Surgery (ileostomy, colectomy, or proctocolectomy):
The time point of the UC-related surgery (ileostomy, colectomy, or proctocolectomy) intercurrent event is defined as the date of the first UC-related surgery. All measurements on or after the date of the UC-related surgery (ileostomy, colectomy, or proctocolectomy) will be handled similarly as UC-related corticosteroid intercurrent events.

For the additional Period 1 efficacy endpoints and Induction Period 2 efficacy endpoints similar methods to address potential intercurrent events will be applied.

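### Sub-Study 2 Period 2 response summaries can count subjects who were already responders at Week 12, and SAP 8.0 leaves unclear whether a Period 1 steroid or surgery event carries into Period 2

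*SAP*

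**What the plan says.** Routing at Week 12 uses the local read. The protocol synopsis says: "Subjects who do not achieve clinical response per Adapted Mayo score (locally read Mayo endoscopic subscore) at Week 12 may be eligible" for Period 2. SAP 2.2 sends to maintenance those who "achieve clinical response per Adapted Mayo score (locally read Mayo endoscopic sub score) after completion of the 12-week Induction Period 1", and adds that "subjects who do not achieve clinical response will be randomized by Interactive Response Technologies (IRT) to Induction Period 2".

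Scoring uses the other read. SAP 3.0 states: "The endoscopic subscore will be based on central readings after adjudication (when applicable". SAP 9.1 takes the last value on or before the first Period 1 dose as the efficacy baseline. A separate Period 2 baseline exists only for laboratory and vital-sign data (SAP 10.3 and 10.4).

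The Period 2 population in SAP 4.0 "includes all subjects who received at least one dose of risankizumab during Induction Period 2 from Sub-Study 2". The Period 2 endpoints in SAP 3.3 include "The achievement of clinical response per Adapted Mayo score at Week 24" and "Time to clinical response per Partial Adapted Mayo". SAP 9.5.2 summarises them descriptively by treatment sequence, using Kaplan-Meier for time to response. It gives no time origin and no risk set for that curve.

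For steroid events (IE2), SAP 8.0 makes the subject a non-responder on binary endpoints from the date of the "intercurrent event through the end of the Induction study in the primary analysis", with hospitalisation and UC-related surgery endpoints exempt. Surgery (IE3) is handled similarly, and similar methods extend to Period 2 endpoints. SAP 9.2.1 adds a non-responder override after imputation.

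**The concern.** Period 2 is meant to show how many Week 12 non-responders gain response on re-induction or on maintenance dosing. That reading needs everyone in the denominator to be a non-responder at the start by the same definition that is used at the end. Here the two definitions use different endoscopy reads, and for one endpoint a different score. Nothing in SAP 4.0 or 9.5.2 excludes, flags or separately reports subjects who already meet the endpoint when Period 2 begins.

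The steroid and surgery rule works the other way. If a Period 1 event counts to Week 24, the subject is a failure on nearly all Period 2 binary endpoints whatever the second treatment does. At stake are the absolute Period 2 rates, the time-to-response curve, and to a small degree the visible difference between sequences.

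**Working it through.** The plan gives no sample size, expected rate, read-discordance rate or steroid-event rate for Period 2, so there is no planned figure to reproduce. The definitions come from SAP 3.0. Adapted Mayo response needs a fall of at least 2 points and at least 30%, plus the rectal bleeding condition (a fall of at least 1, or a value of at most 1). Partial Adapted Mayo response needs a fall of at least 1 point and at least 30%, plus the same condition. Scores below are SFS/RBS/ES (stool frequency, rectal bleeding, endoscopy).

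**Step 1. Read mismatch.**
- Baseline 3/2/3, total 8.
- Week 12 local 2/1/3, total 6: fall 2/8 = 25%, a non-responder who enters Period 2.
- Week 12 central 2/1/2, total 5: fall 3/8 = 37.5%, RBS 1, a responder by the SAP definition.

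This needs a local score at least one point above the central score.

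**Step 2. Score mismatch with identical reads.**
- Baseline 2/1/3, total 6; Week 12 1/1/3, total 5: fall 1 point, an Adapted Mayo non-responder.
- Partial Adapted Mayo goes from 3 to 2: fall 1/3 = 33%, RBS 1, already a responder.

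**Step 3. How often this could arise.** I enumerated all eligible baselines (total 5 to 9, ES 2 or 3) with every non-worsening Week 12 state, equally weighted. This maps the definitions; it does not estimate prevalence.

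| Subscore grid | Non-responder states | Become responders if ES is one lower | Already in Partial Adapted Mayo response |
|---|---|---|---|
| Integer | 210 | 54 (26%) | 32 (15%) |
| Thirds (3-day averages) | 7,252 | 1,394 (19%) | 982 (14%) |

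A simulation with integer subscores and correlated improvement, at 31 to 62% non-response, gave 21 to 30% and 13 to 17% for the last two columns. If the central read is one point lower in 10 to 20% of non-responders (assumed), the share entering as central-read responders is f = 21% × 10% ≈ 2% up to 30% × 20% = 6%.

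**Step 4. Effect on Week 24 response.** Let q be the true conversion rate among real non-responders and r the share of the f group still responding at Week 24.

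Observed rate = (1 − f)q + f·r, so net inflation = f(r − q).

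With r = 80% and q = 35 to 50% (assumed):
- lowest: 2% × (80% − 50%) = 0.6 points
- highest: 6% × (80% − 35%) = 2.7 points

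With f and r equal across arms, a difference shrinks by the factor (1 − f). An assumed 15-point difference loses 15 × 0.02 = 0.3 to 15 × 0.06 = 0.9 points.

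**Step 5. Clinical remission.** In the thirds grid, a local-read non-responder can be in central-read remission only with local ES 3, central ES 0 or 1, and a baseline no higher than 5.67. Carry-over for remission is close to impossible.

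**Step 6. Period 1 steroid or surgery events.** If a share s of ITT2_P2 had such an event in Period 1 and it carries over, the rate falls by s·q. With s = 5% (assumed), 50% becomes 47.5% and 35% becomes 33.25%, so the 15-point difference becomes 14.25. Such subjects can reach Period 2: protocol 5.4.1 requires withdrawal for prohibited medication only when continuing would put the subject at risk.

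**The case against.** The strongest reply is that no inferential result is touched. Protocol 8.1.1.1 calls the Period 2 analysis exploratory, SAP 9.5.2 plans descriptive summaries with no between-arm test, and SAP 13.0 keeps these endpoints outside type I error control. Both statuses precede the 1:1:1 re-randomisation, so they are balanced in expectation across the three re-randomised arms. Analysing everyone dosed is also defensible, because it matches the rule that actually routes patients. All of this stands, and it limits the priority.

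A reader might infer that early central-read responders are guaranteed Week 24 successes. The documents do not support that: SAP 2.2 has a third endoscopy at Week 24, and no rule carries Week 12 status forward. A reader might also take the whole share f as inflation. That would require all of them to keep response and none to have converted otherwise.

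On the steroid rule, a reader might infer that it is an error to be reset at Week 12. That goes too far. Starting or increasing these steroids after baseline is already prohibited (protocol 5.2.3.2), so such an event is a departure from protocol and not planned rescue. Efficacy is measured from Week 0, and not crediting response after a steroid start fits the estimand wording in SAP 2.1. Whether to reset is an estimand choice. What remains is that SAP 8.0 does not define how far the induction study extends and says only that similar methods apply. The literal reading therefore carries the event forward, while a Period 2-only reading is not excluded.

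**Conclusion.** The concern holds in a limited form. ITT2_P2 can include subjects already in Adapted Mayo response by central read, and subjects already in Partial Adapted Mayo response whichever read is used. They inflate the descriptive Week 24 response rate, shorten Period 2 time to response and slightly dilute arm differences, without favouring a re-randomised arm in expectation. The placebo/risankizumab sequence is not a randomised comparator, so no such balance protects comparisons with it.

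The size cannot be derived from the documents. The range of 0.6 to 2.7 points rests wholly on assumed f = 2 to 6%, r = 80% and q = 35 to 50%. Remission is practically unaffected. The Period 1 event rule is an ambiguity to settle. Priority is minor, and the Week 12 primary and secondary results are unaffected.

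**What to change.** 1. In SAP 4.0 and 9.5.2, report Week 24 clinical response in ITT2_P2 subjects who were Week 12 non-responders by the SAP (central-read) definition, beside all ITT2_P2. Week 12 status precedes re-randomisation, so the randomised comparison is preserved. State how subjects without a Week 12 central read are classified, since SAP 2.2 allows entry without endoscopy in COVID-19 or conflict cases.
2. In SAP 9.5.2, count Period 2 time to Partial Adapted Mayo response from the first Period 2 dose, in subjects not already in that response at Week 12.
3. In SAP 8.0, state whether a Period 1 IE2 or IE3 carries into Period 2 endpoints, and tabulate by sequence how many ITT2_P2 subjects it affects. Say the same for censoring in the time-to-response summary: under the SAP 9.5.1 rule such a subject would be censored before the Period 2 clock starts.

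The cost is SAP wording, one flag from data already collected and a short table. The downside is a slightly smaller set for items 1 and 2.

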5.0 Subject Disposition

The total number of subjects who were enrolled, randomized, and treated will be summarized.

A summary of subject accountability will be provided where the number of subjects in each of the following categories will be summarized for each treatment group:

- Subjects randomized in the study
- Subjects who took at least one dose of study drug (ITT2 for the Induction Period 1, ITT2_P2 for the Induction Period 2)
- Subjects who completed study drug (ITT2 for the Induction Period 1, ITT2_P2 for the Induction Period 2)
- Subjects who prematurely discontinued study drug (ITT2 for the Induction Period 1, ITT2_P2 for the Induction Period 2)
- Subjects who completed study (ITT2 for the Induction Period 1, ITT2_P2 for the Induction Period 2)
- Subjects who prematurely discontinued from study (ITT2 for the Induction Period 1, ITT2_P2 for the Induction Period 2)

For end of study participation, the number and percentage of subjects who completed the protocol defined follow-up period (or did not with associated reasons) will be summarized overall and by treatment group.

In addition, the number and percentage of subjects who discontinued study drug or study will be summarized by reason (primary reason and all reasons) for each treatment group and overall within Induction Period 1 and Induction Period 2. The primary reason and all reasons for discontinuation of study or study drug will be summarized as recorded on the eCRF by the following categories:

- Adverse event (AE)
- Lost to follow-up
- Withdraw consent
- Lack of efficacy
- COVID-19 infection
- COVID-19 logistical restrictions
- Logistical problem (geo-political restrictions)
- Other

Subjects may have more than one reason for discontinuing study or study drug, but they will be counted once for the total number of discontinuations. Subjects have only one primary reason for discontinuing study drug or discontinuing from the study.

For subjects whose study participation were impacted by the geo-political conflicts in Ukraine or surrounding area, the detailed reason about how study participation was affected will be summarized.

